5.5. Sample Size and Power Calculations

Since the current study utilizes retrospective deidentified data without ability to recruit to a target, sample size calculations are not applicable. Further, this is a descriptive study without a priori specified hypotheses. However, we examined the precision of the expected XBB.1.5 absolute VE estimates for the outcomes under various scenarios.

(25% of 12 million are pediatric)*(16% uptake)*(60% of doses were Pfizer-BioNTech)

~ 288,000 pediatric XBB doses in California.

The sample size used at start of follow-up was 3 million. Assuming similar absolute VEs to those seen with the BA.4/5 vaccine for symptomatic COVID-19 infections, we could anticipate estimates between 20 and 40%[4]. To assess the precision for a range of outcomes, incidence rates of 50, 100, 1000 and 10,000 cases per 100,000 unvaccinated persons during the study period were considered. A censoring rate of 5% by the end of the study period was used. A uniform vaccination rate between 14 days after study index and the end of follow-up was assumed.

Survival and censoring times were simulated assuming exponential distributions. Vaccination status was modelled as a time-varying covariate[5]. Hazard ratios were input as 1-(VE/100). Simulations were run a minimum of 10 times per scenario. Cox regression models were run on each simulated dataset to estimate the 95% CIs for the log HRs. Means were generated and exponentiated to obtain the 95% CIs for the VEs using (1- HR) x 100 and used to describe VE precision. Simulations were repeated on 25% of the initial sample size to represent the precision in a potential subgroup.

Table 5.4 Simulated 95% Confidence Intervals [Total Number of Events] for BNT162b2 XBB.1.5 Vaccine Effectiveness Estimates

Number at Start of	Vaccine Effectiveness,	Cases per 100,000 Unvaccinated Persons by End of Study			
Follow-up	%	50	100	1000	10,000
3,000,000	20	2, 37 [1488]	7, 32 [2871]	16, 24 [28,678]	19, 21 [274,706]
Ī	30	11, 45 [1429]	17, 41 [2849]	26, 34 [28,475]	29, 31 [272,600]
	40	22, 53 [1418]	29, 51 [2845]	37, 43 [28,256]	39, 41 [270,864]
750,000	20	-24, 49 [361]	-7, 43 [720]	12, 28 [7150]	17, 23 [68,646]
[30	-12, 57 [358]	2, 50 [713]	22, 37 [7097]	28, 32 [68,173]
	40	6, 67 [354]	14, 58 [712]	33, 47 [7077]	38, 42 [67,719]

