Table 5.4 shows that there should be sufficient sample size in the California registry to produce 95% CIs for VEs that exclude 0 for the evaluated VEs and incidence rates, except for the rarer event scenarios in a subgroup. Assuming similar VEs in the two state registries, the inclusion of patients from the Louisiana registry would increase the precision further.

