Table 5.4 shows that there should be sufficient sample size in the California registry to produce 95% CIs for VEs that exclude 0 for the evaluated VEs and incidence rates, except for the rare event scenario in a subgroup. Assuming similar VEs in the two state registries, the inclusion of patients from the Louisiana registry would increase the precision further.

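### The statement that the California sample should give CIs excluding 0 rests on average simulated limits, a rule that can be met at about 50% power, and it is unsupported in a few cells it covers

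*SAP*

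**What the plan says.** The Aim 2 (pediatric) and Aim 1 (adult) SAPs use the same method in Section 5.5. Sample size calculations are declared not applicable and the study descriptive, but expected precision is simulated. Of the inputs, "incidence rates of 50, 100, 1000 and 10,000 cases per 100,000 unvaccinated persons during the study period were considered", and "Hazard ratios were input as 1-(VE/100" for VE of 20, 30 and 40%. For Aim 2, "The sample size used at start of follow-up was 3 million". The adult figure is 8,550,000. A subgroup is taken as 25% of each.

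On the simulation, "Simulations were run a minimum of 10 times per scenario". On the summary, "Means were generated and exponentiated to obtain the 95% CIs for the VEs".

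Both SAPs then conclude that "there should be sufficient sample size in the California registry to produce 95% CIs for VEs that exclude 0 for the evaluated VEs", at every incidence considered. The Aim 2 SAP excepts rarer-event subgroup scenarios, in the plural. The Aim 1 SAP makes the claim "except for the rare event scenario in a subgroup", in the singular. Neither lists the cells it means, and neither gives the probability that one study's CI excludes 0.

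**The concern.** An average interval describes expected width and position. The closing sentences go further and say what the study should produce, namely a CI that excludes 0. Only one dataset will be realised, so that is a statement about the chance of an outcome, and an average limit does not supply it. A cell can pass with its average limit barely clear of 0 although nearly half of all realisations would include 0.

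At stake is how far a reader can rely on Section 5.5. Table 5.2 of both SAPs refers to it where component analyses depend on sample size, and Section 5.3.1 of the Aim 1 SAP refers to it for the low-uptake fallback. A reader who trusts the sufficiency statement could take a CI that includes 0 in a weak cell as evidence of little effect, when the design had a substantial chance of giving that result under the assumed VE.

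**Working it through.** **What the rule guarantees.** On the log HR scale the limit nearer 0 is the estimate plus 1.96 SE. Its mean is ln(HR) + 1.96 SE, which is below 0 when |ln HR|/SE > 1.96. The chance that a single 95% CI excludes 0 on the protective side is Φ(|ln HR|/SE − 1.96). At the boundary this is Φ(0) = 50%, so 50% is the least power at which the rule is met.

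**Reproducing the plan's figure.** The pediatric full-cohort cell at VE 20% and 50 per 100,000 prints 2, 37 with 1,488 events. An independent simulation used the stated inputs, about 182 days of follow-up and 16% uptake. It gave a mean CI of 1 to 36, SE 0.113 and 1,440 events, 3.2% below the printed count. Of 3,000 simulated trials, 52% had a CI excluding 0. A small person-level run of 30 datasets gave a mean CI of −1 to 35, with 43% excluding 0.

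**From the printed intervals.** SE = [ln(1 − lower VE) − ln(1 − upper VE)]/3.92, with HR = 1 − VE/100. Ranges come from moving each printed limit by ±0.5 points.

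- Pediatric full cohort, VE 20%, 50 per 100,000: (−0.0202 + 0.4620)/3.92 = 0.1127; 0.2231/0.1127 = 1.98; Φ(0.02) = 51%.
- Adult subgroup, VE 20%, 100 per 100,000: (−0.0408 + 0.4155)/3.92 = 0.0956; 0.2231/0.0956 = 2.335; Φ(0.375) = 65%.
- Adult subgroup, VE 30%, 50 per 100,000: (−0.1054 + 0.6733)/3.92 = 0.1449; 0.3567/0.1449 = 2.462; Φ(0.502) = 69%.

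| Cell | Printed CI | Chance a CI excludes 0 | Covered by the claim? |
|---|---|---|---|
| Pediatric full, VE 20%, 50 | 2, 37 | 51% (49–53%) | yes |
| Pediatric full, VE 20%, 100 | 7, 32 | 80% (77–83%) | yes |
| Pediatric full, VE 30%, 50 | 11, 45 | 83% | yes |
| Pediatric full, other nine | – | 98% or more | yes |
| Adult full, readable cells | – | 90% or more | yes |
| Adult subgroup, VE 20%, 50 | −3, 39 | 39% | no |
| Adult subgroup, VE 20%, 100 | 4, 34 | 65% (62–68%) | yes |
| Adult subgroup, VE 30%, 50 | 10, 49 | 69% (67–72%) | if the exception is one cell |
| Pediatric subgroup, VE 30%, 100 | 2, 50 | 55% | unclear |
| Pediatric subgroup, VE 40%, 50 | 6, 67 | 48% | unclear |

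One adult full-cohort interval (VE 40%, 100 per 100,000) cannot be read in the available text.

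**Why a cell at 48% can print a CI excluding 0.** The printed means carry simulation noise. The 6, 67 interval centres on 44.3%, not 40%; with SE 0.267 and centred on 40%, its lower limit is 1 − exp(−0.5108 + 1.96 × 0.267), about −1.3%. Likewise 2, 37 centres on 21.4%; centred on 20%, its lower limit is 1 − exp(−0.2231 + 1.96 × 0.1127), about 0.2%. If only the minimum of 10 datasets was run, the mean log limit has a standard error of 0.1127/√10 = 0.036. The mean lower limit in that cell could then fall anywhere from about −7% to +7%.

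**Uptake.** The dose count above the pediatric table is "25% of 12 million are pediatric)*(16% uptake)*(60% of doses were Pfizer-BioNTech", or 9.6% of 3 million (288,000). The printed table is matched by 16%, not 9.6%. At 9.6% the simulation gives −6 to 40 and 33% for the pediatric full-cohort cell at VE 20% and 50, and −1 to 37 and 47% for the adult subgroup cell at VE 20% and 100. The SAPs do not state which share was simulated.

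**The case against.** The best defence is that the study is descriptive, has no hypotheses and sets no power target, and that the means are offered only to describe precision. On that footing Table 5.4 is sound: every printed pediatric full-cohort interval excludes 0, as does every readable adult one, so the closing sentences describe the tables correctly and the method is disclosed. This stands in part. There is no arithmetic error in the table, and an 80% or 90% threshold would be the reviewer's, not the plan's. It does not rescue the wording, because both SAPs choose exclusion of 0 as their own criterion and say the sample should achieve it.

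Louisiana will add precision, but the claim is made for California alone. If Louisiana added information in proportion to its claims population (3.8/19 = 20%, an assumption), the 51% cell would rise to Φ(1.98 × √1.2 − 1.96), about 58%. Reaching 80% there needs SE 0.2231/(1.96 + 0.84) = 0.080, about twice the information.

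A reader might infer three stronger things that the documents do not support. First, that the claim rests on 50% power throughout: 50% is the floor of the rule, and most cells are far above it. Second, that the weak cells are hospitalization, critical illness or mortality: the SAPs assign no outcome to an incidence column. Third, that the sign of the mean limit was settled by 10-run noise: 10 is a stated minimum and the actual number is not given.

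It also stands that each estimate will be reported with its own CI, that the 10-patient and five-events-per-variable rules govern what is analysed, and that no cutoff is taken from Table 5.4.

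**Conclusion.** The point holds in a limited form. The average-CI rule does not assure that the study's CI will exclude 0, and the sufficiency statement is unsupported in two cells it plainly covers (about 51% and 65%). A third (about 69%) is covered if the Aim 1 exception means a single cell. Two pediatric subgroup cells (about 55% and 48%) are as weak although their printed CIs exclude 0, and the Aim 2 exception does not say whether it includes them. Elsewhere in the full cohorts the statement is reasonable.

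These figures take Table 5.4 at face value and use a normal approximation for the log HR; the simulation at 16% uptake agrees. If 9.6% was the intended uptake, the statement is weaker than this, but that depends on an input the SAPs do not give. No planned estimate is affected.

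**What to change.** In Section 5.5 of both SAPs:

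- Add to Table 5.4, for each cell, the probability that a single 95% CI excludes 0. It can be computed from the SEs behind the printed intervals, or from enough simulated datasets to make the proportion stable; state the number run.
- State the vaccine uptake simulated and reconcile it with the dose count printed above the table.
- Reword the closing paragraph to name the cells where exclusion of 0 is not assured: at least the pediatric full cohort at VE 20% and 50 per 100,000, and the adult subgroup at VE 20% and 100 and at VE 30% and 50 per 100,000. Replace the general rare-event exceptions with a list that also settles the two pediatric subgroup cells.

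The cost is a short calculation, or some computing time, and a wording change. The stated precision becomes slightly less favourable. Data, cohort and analyses stay as they are.

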5.6. Missing Data

No imputation for missing values will be performed. Subject to patient counts (Section 5.7.2), missing or 'unknown' values will be reported and analyzed as separate categories and included in the totals.

5.7. Statistical Methodology and Analyses

5.7.1. General Considerations

Descriptive statistics will be used to summarize variables. For categorical variables, the frequency and percentage of patients in each category will be presented. Percentages will be based on the total number of relevant patients. For continuous variables, data will be presented as means, standard deviations, medians, 25th and 75th percentiles, minimums and maximums. Continuous variables may be additionally categorized and analyzed as categorical variables.

No statistical hypotheses are specified and there will be no correction for multiple comparisons.

090177e1a0eb60ea\Approved\Approved On: 11-Jun-2024 17:59 (GMT)

Time in days between two dates will be calculated as (date2 – date1) + 1, where date2 is on or after date1. Where date2 is before date1, time in days between two dates will be calculated as (date2 – date1). Index date will be considered as Day 1. There is no Day 0.

Unless stated otherwise, one year is defined as 365 days, and one month is defined as 30 days.

All data analysis will be conducted using statistical software SAS version 9.4 or R version 4.1.0 or later.

5.7.2. Minimum Sample Size Requirements

In order to maintain patient de-identification, outcomes, covariates and subgroups will have at least 10 patients in each category to be included in the analysis.

In addition, a minimum of five events per variable (the number of degrees of freedom) will be required in each level of the outcome variable in the adjusted Cox regression models to minimize the potential for biased estimates [4]. Note, as an example, a categorical predictor variable with three levels contributes two degrees of freedom.

5.7.3. Index Date, Baseline and Follow-up

The index date for each individual will be defined as the BNT162b2 XBB.1.5 EUA or FDA approval date (Table 5.1). Age and sex will be assessed at index date. The baseline period used to assess other patient characteristics are specified for each covariate in Table 5.3.

Unvaccinated follow-up time will occur from the date of FDA authorization/approval until 13 days after the receipt of vaccination, the outcome of interest, or are censored at the first of the following: 6 months of follow-up, end of medical and/or pharmacy enrollment, receipt of a non-Pfizer BioNTech vaccine. Where mortality is not the outcome of interest, follow-up time will be additionally censored at death. Where mortality is the outcome of interest, follow-up time will be additionally censored at a death not meeting the outcome criteria.

Vaccinated follow-up time will occur from 14 days after the receipt of vaccination until the outcome of interest, or are censored at the first of the following: 6 months of total follow-up (ie, 11 March 2024), end of medical and/or pharmacy enrollment, receipt of a non-Pfizer BioNTech vaccine or receipt of a second BNT162b2 COVID-19 vaccine dose. Where mortality is not the outcome of interest, follow-up time will be additionally censored at death. Where mortality is the outcome of interest, follow-up time will be additionally censored at a death not meeting the outcome criteria.

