the high risk definition, but not included in HealthVerity data and therefore unable to be assessed. Pregnancy is included in the high risk definition, but is an exclusion criteria for each aim in this protocol and therefore is not listed here. Given the nature of administrative claims data,		the high risk definition, but not included in HealthVerity data and therefore unable to be assessed. Pregnancy is included in the high risk definition, but is an exclusion criteria for each aim in this protocol and therefore is not listed here. Given the nature of administrative claims data, obesity, physical inactivity, and smoking are likely

Variable	Data source(s)	Operational definition
Charlson-Deyo Comorbidity Index, ²⁵ operationalized as scores of 0, 1 or 2 using	HV Claims	Assessed using all-available lookback data. Codes are in annex, and conditions are scored as: 1 point for each of: Myocardial infarction CHF Peripheral vascular disease Cerebrovascular disease Dementia Chronic pulmonary disease Connective tissue disease Peptic ulcer disease Mild liver disease Diabetes mellitus without chronic complications 2 points for each of: Hemiplegia Moderate to severe renal disease Diabetes with chronic complications Cancer, including leukemia and lymphoma 3 points for moderate or severe liver disease 6 points for each of: Metastatic carcinoma HIV/AIDS
Receipt of skilled nursing care and/or long-term care facility stay in year prior to index	HV Claims	Codes in Annex
Wellness visit	HV Claims	Codes in Annex
Decreased functional status	HV Claims	Codes in Annex
Influenza vaccination in year prior to index	HV Claims	Vaccines will be enumerated as per section 8.2. Influenza vaccines are recommended annually, and therefore we will measure influenza vaccination in prior year.

Variable	Data source(s)	Operational definition
Pneumococcal vaccination using all-available time prior to index	HV Claims	Vaccines will be enumerated as per section 8.2. Pneumococcal vaccinations are generally not repeated events, and therefore we will use allavailable lookback data to assess receipt.
Herpes zoster vaccination using all-available time prior to index	HV Claims	Vaccines will be enumerated as per section 8.2. Herpes zoster vaccinations are generally not repeated after primary series, and therefore we will use all-available lookback data to assess receipt.
Outpatient visits prior to index	HV Claims	Number of outpatient visit(s) in 180 days prior to index

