5. RESEARCH METHODS

5.1. Study Design

This will be a retrospective cohort study using data from patients who were California or Louisiana residents in the HealthVerity claims database.

Cohort identification will begin from the date of Emergency Use Authorization (EUA) or U.S Food and Drug Administration (FDA) approval for the BNT162b2 formulation. Study follow-up will occur from FDA EUA or approval date until COVID-19 diagnosis or other outcome of interest (hospitalization, emergency department visit, outpatient encounter, end of medical and/or pharmacy enrollment, or death [according to the mortality database]).

The authorization/approval dates for each BNT162b2 formulation that will be used in this study are provided in Table 5.1.

Table 5.1 Timeline of Key BNT162b2 Regulatory Milestones Applicable to Pediatrics

Vaccine formulation	Age group	Event
BNT162b2 monovalent	Age 12 and	September 11, 2023: U.S. Food and Drug
XBB.1.5 COVID-19 vaccine	older	Administration (FDA) approval
	Age 6 months to 11 years	September 11, 2023: FDA emergency use authorization (EUA)
BNT162b2 bivalent BA.4/5 COVID-19 vaccine	Age 12 and older	August 31, 2022: FDA EUA
	Age 5 to 11	October 12, 2022: FDA EUA
	Age 6 months to 4 years	December 8, 2022: FDA EUA

All persons will be considered unvaccinated from date of FDA date of vaccine authorization/approval until, where applicable, 13 days after receipt of vaccine. In order to allow for time after dose for meaningful immunologic protection to accrue, persons will be considered vaccinated 14 days after vaccination.

The following data are available, from 01 December 2018, with varying look-back periods as outlined below to define patient's characteristics, clinical history, risk factors, and healthcare utilization.

The outcomes of interest are medically attended COVID-19, non-COVID-19 respiratory infections, mortality and healthcare resource utilization and are described in Table 5.2.

Main summary measure: VE = (1 - adjusted hazard ratio [aHR]) * 100, comparing vaccinated to unvaccinated persons

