5.2.1. Inclusion Criteria

- Born in 2006-2023 (as age 0-17 years in 2023, owing to the data providing year but not month or day of birth).
- At least six months of pharmacy and medical enrollment in HealthVerity prior to index date (FDA EUA date per age group vaccine). Six months was selected to allow for analysis to include children age <1yr. A gap of up to 30 days will be allowed.
- Have been a State of California/Louisiana resident for at least six months prior to index date (FDA EUA date per age group and vaccine). A gap of up to 30 days will be allowed.

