Variable	Role(s)	Operational definition		
Influenza vaccination in 6 months prior to index	-Descriptive -Covariate	Assessed in 6 months prior to index Yes or No The list of codes is provided in the Protocol Annex		
Pneumococcal vaccination using all-available time prior to index	-Descriptive -Covariate	Assessed using all-available lookback data Yes or No The list of codes is provided in the Protocol Annex		
Herpes zoster vaccination using all-available time prior to index	-Descriptive -Covariate	Assessed using all-available lookback data Yes or No The list of codes is provided in the Protocol Annex		
Outpatient visits prior to index	-Descriptive (continuous and categorical) -Covariate (categorical)	Number of outpatient visits in 180 days prior to index Categorized as: 0, 1 or 2+ The list of codes is provided in the Protocol Annex		
Inpatient admissions prior to index	-Descriptive (continuous and categorical) -Covariate (categorical)	Number of inpatient admissions in 180 days prior to index Categorized as: 0, 1 or 2+ The list of codes is provided in the Protocol Annex		
Emergency department visits prior to index	-Descriptive (continuous and categorical) -Covariate (categorical)	Number of emergency department visits in 180 days prior to index Categorized as: 0, 1 or 2+ The list of codes is provided in the Protocol Annex		
Telehealth visits prior to index	-Descriptive (continuous and categorical) -Covariate (categorical)	Number of telehealth encounters (CPT: 99201-99215) in 180 days prior to index Categorized as: 0, 1 or 2+		
Number of documented SARS-CoV-2 tests in the 180 days prior to index	-Descriptive (continuous and categorical) -Covariate (categorical)	Number of visits in any setting with CPT in 180 days prior to index: 86408, 86409, 0225U, 0226U Categorized as: 0, 1 or 2+		
Prior post- COVID-19 conditions	-Descriptive -Covariate	Assessed using all-available lookback data, any encounter regardless of setting with ICD- 10-CM U09.9 "Post-COVID-19 condition" Yes or No		

Variable	Role(s)	Operational definition
Prior COVID-19 diagnosis	-Descriptive -Covariate	Any encounter with ICD-10-CM code: U07.1 between 90 and 365 days prior to index Yes or No
Prior bivalent BA.4/5 COVID-19 vaccine	-Descriptive -Subgroup	Where the BNT162b2 XBB.1.5 vaccine is the exposure of interest. Using all-available lookback data, received bivalent BA.4/5 COVID-19 vaccine (regardless of brand) prior to index Yes or No The list of codes is provided in the Protocol Annex

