5.7.5. Primary Analyses

Unvaccinated and unvaccinated person-time (Section 5.7.3) for each outcome of interest will be calculated for each patient, summed across all patients and presented in person-months. The total number of patients with each of the outcomes will be presented by BNT162b2 vaccination status at the time of the COVID-19 encounter. Crude incidence rates and 95% confidence intervals (CIs) will be presented as events per 100,000 person-months (or as appropriate) by BNT162b2 vaccination status. The above analysis will be presented overall and may also be presented by month of follow-up for the primary and secondary outcomes.

Unadjusted Cox regression models will be used to generate hazard ratios (HR) and 95% CIs for the effect of the BNT162b2 for each outcome, with BNT162b2 modelled as a time-varying exposure. Crude VE percentages will then be estimated based on (1-HR) x 100, where HR is obtained from the unadjusted model.

For the primary outcome, for each of incidence rates and hazard ratios, an additional stratification of interest will employ an interaction term between exposure and a time-varying calendar time covariate, to allow for separate estimates of incidence and hazard in the predominantly XBB (11 September – 08 December 2023), co-circulation

(09 December 2023 – 05 January 2024) and predominantly JN.1 (January 6, 2024 – end of data collection [March 11, 2024]) eras.

Adjusted Cox regression models will also be used to generate adjusted HRs (aHR) and adjusted VE percentages, with covariates listed in Table 5.3 included as time-fixed covariates. For analyses where the number of events per variable is low (Section 5.7.2), covariates with SMDs <0.1 may be excluded from regression models.

Measures of absolute and relative VE: For each outcome above, where sample size allows, results will be calculated as:

- Absolute VE comparing vaccinated to unvaccinated persons, regardless of prior vaccination
- Relative VE will be calculated for each of the following mutually exclusive subgroups.
 - a. XBB.1.5 vaccinated vs XBB.1.5 unvaccinated persons who received BA.4/5 bivalent vaccine (regardless of brand).
 - b. XBB.1.5 vaccinated vs XBB.1.5 unvaccinated persons who did not receive BA.4/5 bivalent vaccine but did receive at least 2 doses of mRNA vaccine (regardless of brand).
 - XBB.1.5 vaccinated vs never COVID-19 vaccinated (of any formulation or brand).

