		Annex

Variable	Role(s)	Operational definition
Influenza	-Descriptive	Assessed in the year prior to index
vaccination in year	-Covariate	Yes or No
prior to index		The list of codes is provided in the Protocol

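### The Aim 2 SAP measures influenza vaccination over 15 March to 10 September 2023 instead of the protocol's prior year, which weakens adjustment for vaccine-seeking, mainly for absolute VE in children

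*SAP*

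**What the plan says.** - **Index date.** Aim 2 SAP, 5.7.3: "The index date for each individual will be defined as the BNT162b2 XBB.1.5 EUA or FDA approval date (Table 5.1". Table 5.1 gives the same day for both pediatric rows. For ages 6 months to 11 years it reads "September 11, 2023: FDA emergency use authorization (EUA"), and the row for age 12 and older carries an approval on that date.
- **Influenza covariate, Aim 2.** The row in SAP Table 5.3 is "Influenza vaccination in 6 months prior to index", coded yes or no, and serves as both a descriptive variable and a covariate. Section 5.7.1 adds that "one month is defined as 30 days".
- **Influenza covariate, protocol.** Table 5 in Section 8.3 uses a year and gives the reason: "Influenza vaccines are recommended annually, and therefore we will measure influenza vaccination in prior year".
- **Influenza covariate, Aim 1.** The adult SAP's Table 5.3 keeps the year: "Assessed in the year prior to index".
- **Use in the model.** Aim 2 SAP, 5.7.5, fits adjusted Cox models "with covariates listed in Table 5.3 included as time-fixed covariates". When events per variable are low, it allows covariates with an SMD below 0.1 to be left out.
- **Enrollment.** Aim 2 requires 6 months of prior enrollment: "Six months was selected to allow for analysis to include children age <1yr". The SAP does not say that this is why the influenza window was shortened, and gives no other reason.

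**The concern.** A 6-month window can represent an annual vaccine only if it covers the months when the vaccine is given. Because the index is one calendar date, the window is the same for every child and leaves out the autumn and winter before index. A child vaccinated in October 2022 and not again before 11 September 2023 is coded no, the same as a child who was not vaccinated at all. A yes can mean a late 2022-23 dose or an early 2023-24 dose, so the variable also changes meaning.

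Families who take up yearly vaccines may be more likely to take up XBB.1.5, and may differ in how readily they seek care or in their exposure. The outcome is a medically attended encounter, so both could confound VE. Absolute VE is the more exposed estimate. In Table 5.3 prior COVID-19 vaccination has descriptive and subgroup roles only and is not a covariate. The other vaccine covariates are pneumococcal and zoster, which protocol Table 5 describes as generally not repeated. Influenza is thus the only recurring vaccine-uptake measure in the absolute-VE model.

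**Working it through.** **1. Plan's own size figures.** 25% × 12,000,000 = 3,000,000 children, the cohort behind Aim 2 Table 5.4. Then 3,000,000 × 0.16 × 0.60 = 288,000 expected doses, as stated. The point does not depend on this figure, but Table 5.4 gives a scale for bias.

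**2. The windows** (index 11 September 2023, 30-day months, so 6 months = 180 days):

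| Rule | First day | Last day | Days |
|---|---|---|---|
| Aim 2 SAP, 180 days | 15 March 2023 | 10 September 2023 | 180 |
| Protocol and Aim 1, 365 days | 11 September 2022 | 10 September 2023 | 365 |

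The Aim 2 rule loses 365 − 180 = 185 days, from 11 September 2022 to 14 March 2023. With calendar months instead, the window opens on 11 March 2023, which changes little.

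**3. What falls where.** The documents do not state the vaccination season. If the main months are taken as 1 September 2022 to 28 February 2023 (181 days, an assumption), the 6-month window holds 0 of those days and the one-year window holds 171. Aim 5's exclusion criteria treat 1 August to 10 September 2023 as a period of influenza vaccine receipt. That is 41 of the 180 days (23%), so early 2023-24 doses do enter the Aim 2 variable.

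**4. Possible effect on VE.** The documents give no pediatric influenza uptake, so every input here is assumed. Let p1 and p0 be last-season influenza uptake in XBB.1.5-vaccinated and unvaccinated children, and R the outcome ratio for influenza-vaccinated versus other children. With no capture and no other adjuster, the HR is multiplied by

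B = (p1·R + 1 − p1) / (p0·R + 1 − p0).

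With p1 = 0.70, p0 = 0.40 and a true HR of 0.70 (VE 30%):

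- R = 0.8: B = 0.86/0.92 = 0.935; HR = 0.654; VE = 34.6%.
- R = 1.2: B = 1.14/1.08 = 1.056; HR = 0.739; VE = 26.1%.

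The shift is about 4 to 5 points in either direction. Table 5.4's interval at VE 30% in 3,000,000 children is 26 to 34 at 1,000 cases per 100,000 and 29 to 31 at 10,000. The bound is therefore about equal to the half-width in the first case (4 points) and larger in the second (1 point).

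**5. The SMD rule.** SMD = |a − b| / √{[a(1 − a) + b(1 − b)]/2}, where a and b are the recorded prevalences, that is 0.70 and 0.40 times the share of doses captured:

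| Share captured | a | b | SMD |
|---|---|---|---|
| 100% | 0.700 | 0.400 | 0.63 |
| 10% | 0.070 | 0.040 | 0.13 |
| 5% | 0.035 | 0.020 | 0.09 |
| 2% | 0.014 | 0.008 | 0.06 |

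At about 5% capture or less, a strongly imbalanced factor would be reported as negligible imbalance and could be dropped under 5.7.5. At 10% it would not.

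**The case against.** The case for leaving the row alone has several parts.

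- **The window matches the enrollment rule.** Six months gives every child equal lookback, and protocol Section 8.7 lets a SAP modify the plan. This explains the choice but does not require it. Table 5.3 uses all-available lookback for high-risk conditions, pneumococcal and zoster vaccination, and post-COVID conditions in the same children.
- **Other adjustment remains.** Wellness visits, outpatient, emergency and telehealth visits, SARS-CoV-2 tests, prior COVID-19 diagnosis, and pneumococcal and zoster vaccination stay in the model. Relative VE is split by prior COVID-19 vaccination. Negative control outcomes are planned, with optional bias-corrected VE. All of this stands and limits the point, though a significant negative control leads to revising the confounder set, which needs informative variables.
- **Claims miss doses anyway.** Influenza vaccination comes only from claims (protocol Section 8.2), and Section 6 says roster-billed doses, including those given in schools, are lost. A one-year window would also be incomplete, so full adjustment is not attainable.
- **Dropping is optional.** It applies only when events are few, where intervals are already wide, and 5.7.4 reports the maximum SMD across months, which makes a low value harder to reach.

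A reader might infer that pediatric VE loses its main adjustment for vaccine-seeking, or that the window is wholly off-season. The documents support neither. They do not rank the covariates, and Aim 5 treats the last 41 days of the window as a time when influenza vaccine is received.

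**Conclusion.** The point holds as a departure from the protocol that defeats its stated reason for the covariate. That rests on the documents' dates alone: the window is 15 March to 10 September 2023, and a child whose only dose fell in the preceding 185 days is coded no. The consequence is weaker adjustment for vaccine-seeking, mainly in absolute VE.

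Neither the direction nor the size of residual bias can be known from the documents. The 35% to 26% range around a true VE of 30% is an upper bound for the stated inputs (70% versus 40% uptake, outcome ratio 0.8 to 1.2), because it assumes no capture and no help from other covariates. It should not be read as expected bias. Loss of the covariate through the SMD rule is possible at low capture (about 5% or less on these inputs) but is not assured. The row should be corrected before analysis; it does not by itself invalidate Aim 2.

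**What to change.** In Aim 2 SAP Table 5.3, restore the protocol's one-year window for influenza vaccination: any claim from 11 September 2022 to 10 September 2023, using all enrolled time in that year. Add an indicator for children with under 12 months of observed lookback. If the 6-month window is kept, state the reason and what a yes is then meant to represent.

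The cost is a change of SAP wording, one recoded variable and one added indicator; data are held from December 2018. The downside is incomplete influenza history for children with 6 to 11 months of enrollment. The indicator flags this but does not recover the missing doses, and claims will still miss some doses for everyone. The change is confined to the influenza row; protocol Table 5 gives no one-year window for wellness visits, so this argument does not extend to that row.
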